6.7. Concomitant medications/products and concomitant vaccinations

At each study visit, the investigator or delegate should question the subject's parent(s)/LAR(s) about any medications/products taken and vaccinations received by the subject.

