6.7.1. Recording of concomitant medications/products and concomitant vaccinations

The following concomitant medication(s)/product(s)/vaccine(s) must be recorded in the eCRF.

- All concomitant medications/products, except vitamins and dietary supplements, administered during the period starting 30 days following each dose of study vaccine.
- Any concomitant vaccination administered in the period from first study vaccination (Visit 1) and ending at Visit 4.
- Prophylactic medication (i.e., medication administered in the absence of ANY symptom and in anticipation of a reaction to the vaccination).

E.g., an anti-pyretic is considered to be prophylactic when it is given in the absence of fever and any other symptom, to prevent fever from occurring [fever is defined as temperature $\geq 38.0^{\circ}\text{C}/100.4^{\circ}\text{F}$. The preferred location for measuring temperature in this study will be the oral cavity, the axilla and the rectum].

- Any concomitant medications/products/vaccines listed in Section [6.7.2](#).
- Any concomitant medications/products/vaccines relevant to a SAE to be reported as per protocol or administered at any time during the study period for the treatment of a SAE. In addition, concomitant medications relevant to SAEs need to be recorded on the expedited Adverse Event report.
- Any antipyretic administered in the period starting 6 hours before vaccination and ending 12 hours after vaccination.

6.7.2. Concomitant medications/products/vaccines that may lead to the elimination of a subject from per-protocol analyses

The use of the following concomitant medications/products/vaccines will not require withdrawal of the subject from the study but may determine a subject's evaluability in the

per-protocol analysis. See Section 10.4 for per protocol set for analysis of immunogenicity.

- Any investigational or non-registered product (drug or vaccine) other than the study vaccines used during the study period between the first vaccination at Visit 1 to the blood sampling at Visit 4.
- Immunosuppressants or other immune-modifying drugs administered chronically (i.e., more than 14 days) during the study period between Visit 1 to Visit 4. For corticosteroids, this will mean prednisone ≥ 0.5 mg/kg/day, or equivalent. Inhaled and topical steroids are allowed.
- Immunoglobulins and/or any blood products administered during the study period between the first vaccination at Visit 1 to the blood sampling at Visit 4.

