10.5. Derived and transformed data

- A seronegative subject is a subject whose antibody concentration is below the cut-off value.
- A seropositive subject is a subject whose antibody concentration is greater than or equal to the cut-off value. The applicable thresholds are presented in [Table 7](#).
- A seroprotected subject is a subject whose antibody concentration is greater than or equal to the level defining clinical protection. The following seroprotection thresholds are applicable:
 - anti-D antibody concentrations ≥ 0.1 IU/mL.
 - anti-T antibody concentrations ≥ 0.1 IU/mL.
 - anti-HBs antibody concentrations ≥ 10 mIU/mL.
 - anti-poliovirus types 1, 2 and 3 antibody titers ≥ 8 ED50.
 - anti-PRP antibody concentrations ≥ 0.15 μ g/mL.
- Other cut-offs to be considered:
 - anti RV IgA antibody concentration ≥ 90 U/mL.
 - anti-pneumococcal serotypes (1, 3, 4, 5, 6A, 6B, 7F, 9V, 14, 18C, 19A, 19F, 23F) antibody concentrations ≥ 0.35 μ g/mL for the ELISA.
 - anti-PRP antibody concentrations ≥ 1.0 μ g/mL.
- The GMC calculation will be performed by taking the anti-log of the mean of the log concentration transformations. Note that antibody concentrations below the cut-off of the assay will be given an arbitrary value of half the cut-off while antibody concentration above the assay cut-off but below the Limit of Quantification will be given the assay cut-off as value.

Handling of missing data:

Immunogenicity:

- For a given subject and a given immunogenicity measurement, missing or non-evaluable measurements will not be replaced.

Reactogenicity and Safety:

- For analysis of solicited, unsolicited AEs (such as SAEs or AEs by primary MedDRA term), and for the analysis of concomitant medications, all vaccinated subjects will be considered. Subjects who did not report the event or the concomitant medication will be considered as subjects without the event or the concomitant medication respectively.

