10.8. Analysis of safety

The ES will be used for the analysis of safety.

The following calculations will be performed for each group:

The percentage of doses and of subjects reporting at least one symptom (solicited or unsolicited) during the 8 day (Day 1-Day 8) solicited follow-up period post-vaccination will be computed, along with exact 95% CI. The same calculations will be done for symptoms (solicited or unsolicited) rated as grade 3 in intensity, those assessed as causally related to vaccination, those rated as grade 3 in intensity with causal relationship to vaccination and those that resulted in a medically attended visit.

The percentage of doses and of subjects reporting each individual solicited general symptom will be computed, over the 8 day (Day 1-Day 8) solicited follow-up period post-vaccination, along with exact 95% CI. The same calculations will be done for each individual general solicited symptom rated as grade 3 in intensity, those assessed as causally related to vaccination, those rated as grade 3 in intensity with causal relationship to vaccination and those that resulted in a medically attended visit. For fever, additional analyses will be performed by 0.5°C increments. These calculations will also be performed by sex and race.

The verbatim reports of unsolicited AEs will be reviewed by a physician and the signs and symptoms will be coded according to MedDRA. Every verbatim term will be matched with the appropriate Preferred Term. The percentage of subjects with unsolicited AEs occurring within 31 day (Day 1-Day 31) follow-up period after any dose with its exact 95% CI will be tabulated by group, and by preferred term. Similar tabulation will be done for unsolicited AEs rated as grade 3, for unsolicited AEs with causal relationship to vaccination, for unsolicited AEs rated as grade 3 with causal relationship to vaccination and those that resulted in a medically attended visit.

The percentage of subjects who started taking at least one concomitant medication, antipyretic medication and prophylactic antipyretic medication during the 8 day (Days 1-8) and 31 day (Days 1-31) follow-up period post-vaccination will be tabulated by dose, overall per subject and over all the doses.

Subjects who experienced at least one SAE during the entire study period (from Dose 1 till ESFU Contact at Month 10) will be reported and the SAEs will be described in detail.

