6.4. Analysis of safety

6.4.1. Analysis of safety planned in the protocol

The ES will be used for the analysis of safety.

The following calculations will be performed for each group:

The percentage of doses and of subjects reporting at least one symptom (solicited or unsolicited) during the 8 day (Day 1-Day 8) solicited follow-up period post-vaccination will be computed, along with exact 95% CI. The same calculations will be done for symptoms (solicited or unsolicited) rated as grade 3 in intensity, those assessed as causally related to vaccination, those rated as grade 3 in intensity with causal relationship to vaccination and those that resulted in a medically attended visit.

The percentage of doses and of subjects reporting each individual solicited general symptom will be computed, over the 8 day (Day 1-Day 8) solicited follow-up period post-vaccination, along with exact 95% CI. The same calculations will be done for each individual general solicited symptom rated as grade 3 in intensity, those assessed as causally related to vaccination, those rated as grade 3 in intensity with causal relationship to vaccination and those that resulted in a medically attended visit. For fever, additional analyses will be performed by 0.5°C increments. These calculations will also be performed by sex and race.

The verbatim reports of unsolicited AEs will be reviewed by a physician and the signs and symptoms will be coded according to MedDRA. Every verbatim term will be matched with the appropriate Preferred Term. The percentage of subjects with unsolicited AEs occurring within 31 day (Day 1-Day 31) follow-up period after any dose with its exact 95% CI will be tabulated by group, and by preferred term. Similar tabulation will be done for unsolicited AEs rated as grade 3, for unsolicited AEs with causal relationship to vaccination, for unsolicited AEs rated as grade 3 with causal relationship to vaccination and those that resulted in a medically attended visit.

The percentage of subjects who started taking at least one concomitant medication, antipyretic medication and prophylactic antipyretic medication during the 8 day (Days 1-8) and 31 day (Days 1-31) follow-up period post-vaccination will be tabulated by dose, overall per subject and over all the doses.

Subjects who experienced at least one SAE during the entire study period (from Dose 1 till ESFU Contact at Month 10) will be reported and the SAEs will be described in detail.

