11.2. Standard data derivation

11.2.1. Date derivation

- SAS date derived from a character date: in case day is missing, 15 is used. In case day & month are missing, 30June is used.
- Onset day for an event (ae, medication, vaccination, ...): the onset day is the number of days between the last study vaccination & the onset/start date of the event. This is 1 for an event starting on the same day as a vaccination. See SAS date derived in case the start date of the event is incomplete.
- Duration: Duration of an event is expressed in days. It is the number of days between the start & the stop dates + 1. Therefore duration is 1 day for an event starting & ending on the same day.

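### Protocol 6.7.1 starts general concomitant-medication recording 30 days after each dose with no end, which contradicts the planned Day 1-8 and Day 1-31 medication tables

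*Protocol*

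**What the plan says.** Protocol 6.7.1 lists what must be entered in the eCRF. Its only general medication rule covers products "administered during the period starting 30 days following each dose of study vaccine". The same list has narrower rules:

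- prophylactic medication, with no time limit;
- "Any antipyretic administered in the period starting 6 hours before vaccination and ending 12 hours after vaccination";
- medication relevant to or given for an SAE;
- the products in 6.7.2;
- concomitant vaccinations from Visit 1 to Visit 4.

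Protocol 6.7 adds that at each visit staff "should question the subject's parent(s)/LAR(s) about any medications/products taken and vaccinations received by the subject". Protocol 5.6.12 sends the recording rule back to 6.7.

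For the analysis, SAP 6.4.1 repeats Protocol 10.8: "The percentage of subjects who started taking at least one concomitant medication, antipyretic medication and prophylactic antipyretic medication" is reported, and these results "during the 8 day (Days 1-8) and 31 day (Days 1-31) follow-up period post-vaccination will be tabulated by dose". On missing entries, Protocol 10.5 says: "Subjects who did not report the event or the concomitant medication will be considered as subjects without the event or the concomitant medication respectively". SAP 11.2.5 and 11.2.6 keep that rule.

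**The concern.** The recording rule opens on the last day of the longer analysis window and after the shorter one has closed. A site that follows it need not enter an antipyretic given for a non-serious fever on Day 3 after Dose 1. The diary-card instructions in Protocol 5.6.13 cover temperature and adverse events and do not mention medication. Protocol 8.6 requires treatment to be recorded for SAEs only.

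The gap would not show in the output. An infant without an entry is scored as untreated, and SAP 11.2.5 uses all vaccinated subjects as the denominator for concomitant medication. The documented-dose sensitivity analysis in SAP 6.4.2 and 11.2.5 is for solicited symptoms and would not reveal it.

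At stake is the reading of the reactogenicity results. Antipyretic treatment in the first week is useful context for fever and irritability rates. If sites interpret the rule differently, the tables mix two collection rules. Site staff know the allocation (Protocol 5.3), so that discretion rests with unblinded people.

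**Working it through.** The plan gives no figure to reproduce. The check counts the days on which the general rule overlaps the analysis windows.

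**Inputs**
- Day numbering (SAP 11.2.1): "This is 1 for an event starting on the same day as a vaccination". The day 30 days after a dose is therefore Day 30 + 1 = 31.
- Recording start: 30 days after each dose (Protocol 6.7.1). No end is given.
- Analysis windows: Days 1-8 and Days 1-31 (Protocol 10.8, SAP 6.4.1).
- Vaccination visits: three, with HRV vaccine at the first two (Protocol Table 4).
- Intervals: 60 days optimal (Protocol Table 5). Table 19 allows 49-83 days from Visit 1 to Visit 2 and 56-83 days from Visit 2 to Visit 3.

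**Two literal readings**
- Reading A: each dose's window closes at the next dose. A day counts as covered if it is at least 30 days after the most recent dose.
- Reading B: no window closes, as no end is written. A day counts as covered if it is at least 30 days after any dose.

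Under Reading B, the Dose 1 window opens on Day 31. Dose 2 comes at least 49 days after Dose 1, so every day after Dose 2 is already inside the Dose 1 window.

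| Days covered by the general rule | Reading A, 8-day | Reading A, 31-day | Reading B, 8-day | Reading B, 31-day |
|---|---|---|---|---|
| After Dose 1 | 0/8 | 1/31 | 0/8 | 1/31 |
| After Dose 2 | 0/8 | 1/31 | 8/8 | 31/31 |
| After Dose 3 | 0/8 | 1/31 | 8/8 | 31/31 |
| Two HRV doses | 0/16 = 0% | 2/62 = 3.2% | 8/16 = 50% | 32/62 = 52% |
| Three vaccination visits | 0/24 = 0% | 3/93 = 3.2% | 16/24 = 67% | 63/93 = 68% |

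The counts are the same at intervals of 49/56, 60/60 and 83/83 days.

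**What Reading B does to the by-dose table.** Suppose the true share of infants starting a given medication is u after both HRV doses. Apart from the separate rules, the Dose 1 row would show close to zero and the Dose 2 row would show u. The rise would come from the recording rule alone.

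**What the separate rules add.** After each dose, the antipyretic rule covers 12 of 8 × 24 = 192 hours (6.25%) and 12 of 31 × 24 = 744 hours (1.6%). Prophylactic antipyretics are recorded whatever the window. For antipyretics, what remains uncovered is therapeutic use from 12 hours after vaccination to Day 30. Under Reading A this applies after every dose, and under Reading B after Dose 1 only.

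**With the window set to the dose day plus 30 days,** coverage is 8/8 and 31/31 after every dose.

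**The case against.** The best reply is that this is a drafting slip that few sites would follow. Staff ask about any medication at each visit. Table 4 marks the recording of concomitant medication for the eCRF at Visits 1 to 4. The unsolicited-AE period is the vaccination day plus the next 30 days (Protocol 5.6.13 and 8.3.1). Reading A also fits the schedule badly: Visit 4 is planned 30 days after Dose 3, so the Dose 3 window would last about one day. The eCRF instructions, which are not in these documents, may already be correct. All of this stands as evidence of intent. It does not remove the contradiction, because no passage overrides the bullet and 5.6.12 points back to it.

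A reader might infer that the medication tables would lose most of their data, or be close to empty. The documents do not support that. It needs every window to close at the next dose, which the text does not say. With the window left open, about half of the HRV-dose days are covered. Prophylactic antipyretic use, one of the three planned tabulations, has its own rule and is not lost.

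A reader might also infer that the fever results are compromised. Fever and irritability come from diary cards and are collected regardless of 6.7.1. No planned analysis adjusts them for antipyretic use, so what is weakened is context for interpretation. Concomitant medication is neither an objective nor an endpoint, and Protocol 10.9 makes these tables descriptive.

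**Conclusion.** The point holds as an inconsistency in an operative data-collection rule. On the literal text, the general rule misses all of Days 1-8 and 30 of 31 days after Dose 1. Whether later doses are affected depends on an end that the bullet does not give, so coverage over the two HRV doses ranges from 0% to 50% (8-day) and from 3% to 52% (31-day).

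These are shares of days on which recording is required. They are not shares of medications lost, for which the documents give no basis. They assume that sites apply the bullet as written. The three-visit figures also assume that recording reaches Day 31 after Dose 3, although Table 19 allows Visit 4 from 21 days.

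The loss falls on medication without a rule of its own, chiefly therapeutic antipyretics from 12 hours to Day 30, and it would bias the tabulated rates downward. The non-inferiority tests, the per-protocol set and the sample size are not affected. It should be corrected, but it does not threaten the trial's confirmatory conclusions.

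**What to change.** Reconcile Protocol 6.7.1 with Protocol 10.8 and SAP 6.4.1. State that all concomitant medications and products, with the existing exception for vitamins and dietary supplements, are recorded from the day of each study vaccine dose through 30 days after that dose (Day 1 to Day 31). Leave the separate rules as they are, and align the eCRF completion guide.

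The cost is one sentence in the protocol and a matching line in the guide. Any site that has followed the literal text will record somewhat more medications. No analysis in the SAP needs to change.

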7. HEALTH ECONOMICS

Not applicable.

8. SAFETY

The investigator or site staff is/are responsible for the detection, documentation and reporting of events meeting the criteria and definition of an AE or SAE as provided in this protocol.

Each subject's parent(s)/LAR(s) will be instructed to contact the investigator immediately should they/the subject manifest any signs or symptoms they perceive as serious.

8.1. Safety definitions

8.1.1. Definition of an adverse event

An AE is any untoward medical occurrence in a clinical investigation subject, temporally associated with the use of a medicinal product, whether or not considered related to the medicinal product.

An AE can therefore be any unfavourable and unintended sign (including an abnormal laboratory finding), symptom, or disease (new or exacerbated) temporally associated with the use of a medicinal product. For marketed medicinal products, this also includes failure to produce expected benefits (i.e., lack of efficacy), abuse or misuse.

Examples of an AE include:

- Significant or unexpected worsening or exacerbation of the condition/indication under study.
- Exacerbation of a chronic or intermittent pre-existing condition including either an increase in frequency and/or intensity of the condition.
- New conditions detected or diagnosed after study vaccines administration even though they may have been present prior to the start of the study.
- Signs, symptoms, or the clinical sequelae of a suspected interaction.
- Signs, symptoms, or the clinical sequelae of a suspected overdose of either study vaccines or a concurrent medication (overdose per se should not be reported as an AE/SAE).
- Signs, symptoms temporally associated with study vaccines administration.
- Significant failure of expected pharmacological or biological action.
- Pre- or post-treatment events that occur as a result of protocol-mandated procedures (i.e., invasive procedures, modification of subject's previous therapeutic regimen).

AEs to be recorded as endpoints (solicited AEs) are described in Section 8.1.3. All other AEs will be recorded as UNSOLICITED AEs.

Examples of an AE DO NOT include:

- Medical or surgical procedures (e.g., endoscopy, appendectomy); the condition that leads to the procedure is an AE/SAE.
- Situations where an untoward medical occurrence did not occur (e.g., social and/or convenience admission to a hospital, admission for routine examination).
- Anticipated day-to-day fluctuations of pre-existing disease(s) or condition(s) present or detected at the start of the study that do not worsen.
- Pre-existing conditions or signs and/or symptoms present in a subject prior to the study vaccination. These events will be recorded in the medical history section of the eCRF.

8.1.2. Definition of a serious adverse event

A SAE is any untoward medical occurrence that:

- a. Results in death,
- b. Is life-threatening,

Note: The term 'life-threatening' in the definition of 'serious' refers to an event in which the subject was at risk of death at the time of the event. It does not refer to an event, which hypothetically might have caused death, had it been more severe.

- c. Requires hospitalization or prolongation of existing hospitalization,

Note: In general, hospitalization signifies that the subject has been admitted at the hospital or emergency ward for observation and/or treatment that would not have been appropriate in the physician's office or in an out-patient setting. Complications that occur during hospitalization are also considered AEs. If a complication prolongs hospitalization or fulfills any other serious criteria, the event will also be considered serious. When in doubt as to whether 'hospitalization' occurred or was necessary, the AE should be considered serious.

Hospitalization for elective treatment of a pre-existing condition (known or diagnosed prior to informed consent signature) that did not worsen from baseline is NOT considered an AE.

- d. Results in disability/incapacity, OR

Note: The term disability means a substantial disruption of a person's ability to conduct normal life functions. This definition is not intended to include experiences of relatively minor medical significance such as uncomplicated headache, nausea, vomiting, diarrhea, influenza like illness, and accidental trauma (e.g., sprained ankle) which may interfere or prevent everyday life functions but do not constitute a substantial disruption.

Medical or scientific judgement should be exercised in deciding whether reporting is appropriate in other situations, such as important medical events that may not be immediately life-threatening or result in death or hospitalization but may jeopardise the subject or may require medical or surgical intervention to prevent one of the other

outcomes listed in the above definition. These should also be considered serious. Examples of such events are invasive or malignant cancers, intensive treatment in an emergency room or at home for allergic bronchospasm, blood dyscrasias or convulsions that do not result in hospitalization.

8.1.3. Solicited adverse events

8.1.3.1. Solicited general adverse events

The following general AEs will be solicited (Table 11):

Table 11 Solicited general adverse events

Fever
Irritability/Fussiness
Diarrhea
Vomiting
Loss of appetite
Cough/runny nose

Note: Parent(s)/LAR(s) will be instructed to measure and record the oral, axillary or rectal body temperature in the evening. Should additional temperature measurements be performed at other times of day, parent(s)/LAR(s) will be instructed to record the highest temperature in the diary card.

8.1.4. Clinical laboratory parameters and other abnormal assessments qualifying as adverse events or serious adverse events

In absence of diagnosis, abnormal laboratory findings (e.g., clinical chemistry, hematology, urinalysis) or other abnormal assessments (e.g., vital signs etc) that are judged by the investigator to be clinically significant will be recorded as AE or SAE if they meet the definition of an AE or SAE (refer to Sections 8.1.1 and 8.1.2). Clinically significant abnormal laboratory findings or other abnormal assessments that are present at baseline and significantly worsen following the start of the study will also be reported as AEs or SAEs.

The investigator will exercise his or her medical and scientific judgement in deciding whether an abnormal laboratory finding or other abnormal assessment is clinically significant.

